unknown. Therefore, we will develop a population firing-rate circuit model of pain processing in the spinal cord. We will use the direct neural response to SCS from Aim 2 as the inputs to our circuit model. We will determine what types of spinal cord modulation best correlate with experimental measurements of pain modulation during SCS.

Exploratory Aim: Model-based optimization of SCS

Due to our poor scientific understanding of how SCS works and the limited individualization of this therapy, we hypothesize that current clinical implementation of SCS is suboptimal. Therefore, in this exploratory analysis, we will use our computational models to identify stimulation protocols (e.g., alternative waveform parameters) that may improve the desired physiological effects and corresponding pain relief.

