2. BACKGROUND AND RATIONALE

2.1 Background on Condition, Disease, or Other Primary Study Focus

SCS was first tested in patients in 1967, two years after Melzack and Wall published the gate control theory of pain.^{16,17} Conventional SCS involves tonic electrical stimulation at a moderate frequency (e.g., 40-60 Hz) with the goal of exciting large-diameter ($A\beta$) sensory afferents in the dorsal columns to create paresthesias (e.g., tingling, buzzing, pin and needles, pressure) over the painful areas (Fig. 2.1A).¹⁸ According to the gate-control theory, some of the $A\beta$ fibers have collaterals that project to the affected spinal levels. SCS results in antidromic activation of the $A\beta$ fibers that in turn (via their collaterals) lead to inhibition of nociceptive-specific or wide dynamic range projection neurons in the dorsal horn (Fig. 2.1). In neuropathic pain conditions, excessive nociceptive inputs are believed to produce hyperexcitability in these projection neurons (i.e., central sensitization). Antidromic activation of $A\beta$ fibers from SCS is hypothesized to inhibit output from these projection neurons largely through the activation of inhibitory interneurons that help close the “gate” and prevent the transmission of pain signals to the brain.¹⁹ There is additional experimental evidence that orthodromic $A\beta$ axonal activation may also help reduce pain via supraspinal mechanisms, such as descending inhibition.²⁰

Stimulator programming involves assessing a variety of parameter combinations (e.g., amplitude, pulse width, frequency, stimulation configuration) with the goal of maximizing the overlap of SCS-induced paresthesias with a patient’s painful areas. Clinical experience suggests that sufficient pain-paresthesia overlap increases the likelihood for pain relief.²¹ It is important to note, that SCS-induced pain relief occurs over a time course of seconds to several hours. However, SCS-induced paresthesias occur rapidly (~1 s) and serve as a surrogate for pain relief that make it practical to test several sets of stimulation parameters within a standard clinical visit. Although widely used for decades, the success rate of SCS, defined as the proportion of patients receiving $\geq 50\%$ pain relief, is approximately 58%.²²

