After participants have received approximately 7 days of 50 Hz SCS, we will perform the study procedures listed below. After performing these study procedures, the participant's SCS system will be returned to the clinically-effective stimulation settings that were previously determined through standard-of-care procedures.

- Collect vital signs (heart rate, blood pressure, respiration rate, body temperature, height and weight)
- Review and record any changes in concomitant medications
- Rate participants current pain on a scale Visual Analog Scale (VAS) and SFMPQ
- Collect
 - Pain disability Index (PDI)
 - Short Form McGill Pain Questionnaire (SFMPQ)
 - Michigan Body Map (MBM)
 - PainDETECT
 - Brief Pain Inventory (BPI)
 - Visual Analog Scale (VAS) and SFMPQ
 - Coping Strategies Questionnaire (CSQ)
 - Fibromyalgia Survey Questionnaire (FSQ)
- Conditioned Pain Modulation (CPM) Test – Assessment to examine how the body naturally controls pain
- Measure participant's sensitivity to different stimuli
 - Vibrometer Test
 - Algometer Test
 - PinPrick Test (Temporal summation)
 - Multimodal Automated Sensory Test (MAST)
- Stimulator programming
 - Perception threshold
 - Discomfort threshold
 - Paresthesia mapping

- Documentation of any adverse events
- Study debriefing

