sequences (crossover design) (Fig. 3.1). We will perform testing before the start of the randomization and at the end of each seven-day treatment period. Subjects will be blinded during programming. To ensure proper blinding, we will set the amplitude of stimulation so that patients do not feel any stimulation-induced paresthesias (except for 50 Hz SCS which requires paresthesias).² Sham SCS will be performed by setting the amplitude to 0 mA.² For some systems, if the stimulation amplitude is decreased to 0 mA, the system will report that the stimulation is OFF and the participants will know that they are not receiving stimulation. Therefore, for these systems, we will perform sham SCS by setting the stimulation parameters to their minimal values: pulse width (~20 μ s), frequency (~2 Hz), and amplitude (~0.1 mA).

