Spinal Segmental Sensitivity. We will assess spinal segmental sensitivity using a manual vibrometer⁶³ and a pressure algometer^{64,65} at the primary pain site (Fig. 9.3). The primary pain site is defined as the area of maximum pain intensity (i.e., the area of worst possible pain) as reported by the patient. If severe hyperalgesia or allodynia prevents testing of the primary pain site, we will select an adjacent, less sensitive pain area. We will also perform testing at mirror sites (site directly opposite to the tested pain site) and/or bilaterally at several control sites (e.g., trapezius, lateral epicondyle, forearm). We will perform testing with the subject resting in a stationary position (e.g., sitting, supine, prone) to reduce the possibility of postural compression of the nerves being tested.

We will use a handheld vibrometer (VSA-3000, Medoc Inc., Ramat Yishai, Israel) with a 1 cm² circular probe (Fig. 9.3A) to deliver vibratory, non-painful stimuli to determine sensitivity to vibration. We will apply an ascending series of vibratory stimuli. Subjects will report the first

sensation of vibration (denoted as vibratory threshold). We will average the vibratory thresholds across two or three consecutive trials at each site separated by intervals of approximately 20 to 60 seconds. We may also apply a random sequence of fixed intensity vibratory stimuli, 1-3 times each, to the individual sites.

[figure not shown]

Figure 9.3. Spinal segmental sensitivity assessed using a (A) Vibrometer and a (B) Algometer. TS is assessed using a (C) PinPrick stimulator.

We will use a handheld, analog pressure algometer (FPK Algometer, Wagner Instruments, Greenwich, CT) with a 1 cm² flat rubber probe (Fig. 9.3B) to deliver pressure-pain stimuli. We will increase the pressure at a rate of approximately 0.30 kg/cm² or 30-50 kPa/s (100 kPa/s maximum rate), to a maximum of 10 kg/cm². Subjects will report their first sensation of pain (pressure-pain detection threshold) and pressure-pain tolerance. We will average the pressure-pain thresholds and pressure-pain tolerance across two or three consecutive trials at each site separated by intervals of approximately 20 to 60 seconds. We may also apply a random sequence of fixed intensity pressures, 1-3 times each, to the individual sites. We will ask the subjects to report the pain intensity of the pressure stimuli using a VAS or a 0-100 NRS.

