Exploratory analyses: To investigate the anti-nociceptive effects of SCS, we are proposing to conduct an exploratory, mechanistic, placebo-controlled study in 25 patients undergoing SCS for chronic pain. We will use quantitative sensory testing (QST) to assess spinal and supraspinal pain processing. In addition to the primary outcome described in Section 9.4.2, we will perform several exploratory analyses. We will evaluate the effects of somatosensory stimuli using static QST measures of sensory detection threshold, pain threshold, and/or tolerance to stimuli (i.e., vibratory threshold, pressure-pain threshold). We will also assess dynamic central pain-processing mechanisms, such as endogenous pain inhibition, by measuring pain sensitivity concurrent with the application of a conditioning stimulus (i.e., conditioned pain modulation (CPM)).¹⁵ Furthermore, we will obtain outcome measures to assess changes in pain intensity, pain quality, pain spread, and quality of life. Additional exploratory outcomes will include patient-reported VAS ratings for back, leg, and general pain,^{1,2} and several self-reported patient questionnaires, such as the Short-Form McGill Pain Questionnaire to assess quality of pain,³ Michigan Body Map to quantify the degree of widespread body pain,⁴ EQ-5D to characterize quality of life,⁵ Pain Disability Index (PDI) to measure pain-related disability,⁶⁸ and questionnaires from the Patient Reported Outcomes Measurements Information (PROMIS)⁶. We will identify responders as patients who demonstrate a $\geq 50\%$ reduction in average pain intensity (as measured by the VAS) with active SCS as compared to sham stimulation, a standard criterion for success with SCS.²² We hypothesize that patients who respond to specific types of SCS will show decreased spinal segmental sensitivity, particularly decreased vibration sensitivity and pressure-pain sensitivity. We believe that effective SCS will also modulate dynamic central pain-processing mechanisms. We hypothesize that effective types of SCS (i.e., patients who show $\geq 50\%$ reduction in average pain intensity) will reduce TS (primary outcome) and improve inhibitor CPM.

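### Visit 6 order implies pain-site vibration thresholds are taken with 50 Hz paresthesia present, so masking could produce the hypothesised decrease for 50 Hz versus Sham

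*Combined protocol and SAP*

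**What the plan says.** **Timing.** For the final visit, section 6.2 states: "After participants have received approximately 7 days of 50 Hz SCS, we will perform the study procedures listed below". Only after those procedures is it planned that the participant's "SCS system will be returned to the clinically-effective stimulation settings that were previously determined through standard-of-care procedures". Section 6.2.2 is consistent with this: "We will perform testing before the start of the randomization and at the end of each seven-day treatment period". Sections 5.1 and 5.4 interrogate the stimulator after testing, to confirm that the settings were not altered.

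**Paresthesia.** Amplitudes are set so that no paresthesia is felt, "except for 50 Hz SCS which requires paresthesias" (6.2.2). Sections 5.1 and 6.2.3 place the 50 Hz paresthesia over the painful areas, and section 2.1 describes such sensations as including tingling and buzzing.

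**Measurement.** In section 9.5.2 the vibrometer is used to "deliver vibratory, non-painful stimuli to determine sensitivity to vibration". It is applied at the primary pain site in an ascending series, and the participant reports the first vibration felt. Mirror and/or control sites are also tested.

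**Hypothesis.** Section 9.6 expects that patients who respond to specific types of SCS "will show decreased spinal segmental sensitivity, particularly decreased vibration sensitivity and pressure-pain sensitivity". A responder has at least a 50% fall in VAS pain on active stimulation compared with sham. The section does not say whether responders' vibration thresholds are compared with their own Sham values or with those of non-responders.

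**Related background.** Section 2.1 reports clinical experience that "sufficient pain-paresthesia overlap increases the likelihood for pain relief".

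**The concern.** A detection threshold depends on what else is felt at the test site. If 50 Hz is on, the participant has to pick out a faint vibration on skin that already tingles or buzzes. The threshold can then rise whether or not pain processing has changed. A higher threshold is lower vibration sensitivity, which is the hypothesised direction.

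Only one of the four conditions is affected, so the within-person comparison does not cancel the effect. The 50 Hz versus Sham contrast carries it in full.

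A second route runs through response. If better overlap of paresthesia with pain gives both more relief and more masking, responders would show higher vibration thresholds than non-responders with no direct link between the two. The overlap statement in 2.1 makes this plausible but does not quantify it.

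Sections 6.2.3 and 9.2 acknowledge a possible order effect from placing 50 Hz last. The documents do not discuss paresthesia affecting a sensory threshold, and they give no analytic use for the mirror or control sites.

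**Working it through.** **1. The plan's own figure.** Section 9.2 gives n = 20 (25 less 20%: 25 × 0.8 = 20), two-sided 5%, 80% power and d_z = 0.68, for temporal summation. Exact noncentral-t power for a paired test has noncentrality d_z × √n on n − 1 df. At n = 20 the detectable d_z is 0.66, power at 0.68 is 82.2%, and power at 0.89 is 96.5% (the plan says above 95%). The figure reproduces. The documents give no figure for vibration thresholds, so the same n is carried over as an illustration.

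**2. Is 50 Hz on during testing?** Three texts point the same way: settings are returned after the Visit 6 procedures; the stimulator is interrogated after testing to show that settings were unaltered; and the aims (1.3) refer to "experimental measurements of pain modulation during SCS". No text states the stimulator state during sensory testing. On is a strong inference, not a stated fact.

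**3. 50 Hz versus Sham with masking only.** Assume no true change and a masking shift m. In SDs of the paired difference, d_z = m. If m is in per-measurement within-person SDs, d_z = m/√2, because the difference of two measurements has SD √2 times as large.

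| Assumed shift m | Noncentrality m√20 | P(significant), m in SD of difference | d_z = m/√2 | P(significant), m in per-measurement SD |
|---|---|---|---|---|
| 0.30 | 1.34 | 25% | 0.21 | 15% |
| 0.50 | 2.24 | 56% | 0.35 | 32% |
| 0.66 | 2.95 | 80% | 0.47 | 51% |

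If only responders are compared with their own Sham values, n is smaller. The success rates of 51% and 58% in section 2.1 give 0.51 × 20 = 10.2 and 0.58 × 20 = 11.6, so about 10 to 12 people. At m = 0.5 SD of the difference the probability is then 29% to 35%.

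**4. Responders versus non-responders.** With equal masking in both groups, the two-sided test rejects in about 5% of trials, 2.5% in the hypothesised direction. That is nominal.

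For unequal masking, simulate 20 people with 55% responders (between the two rates above). Let overlap be normal and correlate r with both relief and the masking shift, with no other link between them. Relief and masking then correlate r², and a two-sample t test is falsely positive as follows.

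| r (assumed) | r² | False positives |
|---|---|---|
| 0.3 | 0.09 | about 6% |
| 0.5 | 0.25 | about 13% |
| 0.7 | 0.49 | about 42% |

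At r = 0.5 and 0.7 nearly all of these are in the hypothesised direction.

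**The case against.** **The responder claim can be pushed too far.** A reader might infer that masking alone would confirm the hypothesis in responders. The documents do not support that. 50 Hz is meant to cause paresthesia in every participant, so masking is expected in non-responders too, and equal masking leaves that test nominal. The bias needs greater masking in responders, which no document quantifies. This stands.

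**Each waveform has its own contrast.** Section 9.1 specifies treatment-level estimates and contrasts, and for the primary outcome 9.2 names each active form against Sham. Burst and 1 kHz versus Sham are therefore not contaminated by masking under 50 Hz. This also stands, and it limits the reach of the point.

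**Masking may count as an effect of SCS.** Section 1.1 asks how SCS alters sensory processing, and section 2.1 attributes paresthesia to the same large-diameter afferents through which SCS is thought to work. A raised threshold under 50 Hz is a legitimate observation. What does not follow is reading it as reduced segmental sensitivity linked to pain relief, which is how 9.6 frames it.

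**Aim 1 does not hang on vibration.** A reader might infer that Aim 1's mechanistic conclusion would rest on an artefact. Its hypothesis in 1.3 names temporal summation, conditioned pain modulation and pain sensitivity, not vibration detection, and vibration is one of many exploratory measures. This stands.

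**Other material may settle the stimulator state.** The Manual of Operations and the scripted test instructions are not among the documents and may specify it. That is a reason to state it in the protocol.

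**Conclusion.** The point holds in a limited form. On the natural reading of the Visit 6 order, pain-site vibration under 50 Hz is measured with paresthesia present, and under the other three conditions without it. Masking could by itself produce the hypothesised decrease for 50 Hz versus Sham, and the plan as written cannot tell it from an anti-nociceptive effect.

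The size is conditional. For assumed shifts of 0.3 to 0.66, the chance of a significant 50 Hz versus Sham result ranges from 15% to 80%, depending on the shift and on which SD it is expressed in. For responders versus non-responders, the false-positive rate runs from nominal under equal masking to about 42% at r = 0.7. Neither the masking size nor the correlations come from the documents.

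The scope is the 50 Hz part of one exploratory hypothesis. Neither the primary temporal summation outcome nor the Burst and 1 kHz contrasts are part of this point. It is still worth correcting: the hypothesis is named and directional, the bias runs its way, and the unnamed comparator leaves room to choose the more vulnerable comparison after seeing the data.

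**What to change.** In section 9.6:

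- Base the pain-site vibration hypothesis, including the responder comparison, on Burst and 1 kHz versus Sham. State whether responders are compared with their own Sham values or with non-responders.
- Report 50 Hz versus Sham for pain-site vibration separately, labelled *measured with paresthesia*. Show the responder comparison with 50 Hz added only as a sensitivity analysis.
- For 50 Hz, add a pain-site versus control-site (or mirror-site) contrast from the sites already tested under 9.5.2. A rise confined to sites with paresthesia would be compatible with masking.
- Use the paresthesia drawings only as a rough guide to which sites are covered. Section 9.5.2 has them made at perception threshold, so they need not match coverage at the treatment amplitude. Because 50 Hz is aimed at the painful areas, nearly all pain sites should fall inside them.

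In section 6.2 and on the case report form, record the stimulator state during sensory testing.

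The cost is analysis wording and one recorded field, with no change to stimulation settings, visits or sample size. The downside is that 50 Hz contributes less to this exploratory hypothesis.

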6.2.1 Screening Evaluation

This study will occur at a single site, the University of Michigan. We will actively and passively recruit participants. We will actively recruit patients from clinics at the University of Michigan (UM), such as clinics in the Department of Anesthesiology and the Department of Neurosurgery. These departments will have access to the purpose of the study, intended patient population, and inclusion/exclusion criteria. For this study, we will consider chronic pain patients who are being treated with SCS from their own doctors as part of their standard clinical care. For active recruitment, our team of pain specialists (e.g., anesthesiologists and/or neurosurgeons) and other study personnel at UM will identify potential candidates and inform them about the study. The study coordinator or a person from the study team will contact the candidates (e.g., via telephone) to discuss details about the study (e.g., eligibility determination) and/or to verify interest. The necessary contact information (e.g., telephone number) of the candidates will be obtained by searching appointment logs and/or medical records.

For passive recruitment, we will post publicly accessible flyers and brochures throughout UM Clinics, and also in various locations around Michigan Medicine (e.g., University Hospital). We will also post flyers and brochures across various other Pain Clinics and Hospitals in Livingston, Washtenaw, and/or Wayne County. IRB-approved flyers and brochures will be hung in several locations (e.g., waiting areas) in these clinics and hospitals. These flyers will have contact information of the study team (e.g., email, phone) and will also have a description of the study (resource included in Section 8-1.8 of the IRB application). Interested candidates may initiate contact with the study team.

Potential subjects who are interested in participating in the study will be contacted by a member of the study team responsible for enrollment to assess interest and eligibility. Interested candidates will have the study and the eligibility criteria explained to them. If, at this point, they wish to continue with enrollment the candidate will be invited to participate in a study screening visit. Screening will be done over phone to verify eligibility. For eligible candidates, we will schedule an enrollment visit and/or other subsequent visits. We may also email candidates the consent forms to study and think about participation. For interested and eligible candidates, we will schedule the enrollment visit and/or other subsequent visits. All potential subjects will be assigned a unique screening ID. Those volunteers who do not meet the eligibility criteria or who choose not to participate in the study at either the telephone Pre-Screen or the Screening Visit will be logged. Personal identifiers will be kept until the study has been closed to recruitment, at which time they will be destroyed. This will prevent repeat screenings of potential participants.

Consenting Procedure

The research team will adopt an optional electronic informed consent procedure using SignNow. This option will be the preferred method for obtaining consent. A study team member will reach out to a candidate over the telephone to discuss the study and obtain consent with the patient over the phone using SignNow. The consent form will be read to the participant and time will be allowed for questions or if the patient would like to read/review the consent form on their own. All candidates will receive an electronic copy of the consent form after signing. If a candidate does not have access to the internet the following steps will be taken.

The screening visit will begin with the informed consent interview. During the consent interview we will explain the study verbally and in writing. If interested, candidates will sign an informed consent, and will be given a copy. The other signed consent form will be placed within the study binder. We will conduct the consent interview in a private setting (e.g., examination

room, office), allowing sufficient time for prospective subjects to make an informed decision. Furthermore, we will also offer candidates the option of taking the informed consent form home to study and think about participation, with a follow up with one of the investigators or study personnel. Once the subject has formally consented to participate they will undergo a screening examination by a member of the study team. After the screening visit, study personnel will follow up with the patient after consent and screening to schedule all research visits.

It is important to note that we will withhold information regarding the type of treatment (i.e., different forms of active stimulation vs. sham), and the order of treatment the subjects will receive during the study (concealment). Instead, we will inform subjects that we are adjusting the settings on their SCS device. We will inform candidates that the purpose of this study is to investigate the physiological effects and potential mechanisms of action of different types of SCS. We will also explain to each candidate that there will be no expected benefit to him/her by participating in this research study. However, it is possible (although not anticipated) that during this research new stimulator settings may be found that could be beneficial. We will also explain that the knowledge gained from this research may be beneficial for others, society, and/or science.

Note: We will debrief subjects at the conclusion of their last research visit (i.e., Visit 6). Concealment is necessary to conduct this research study to avoid potential for altering subject behavior such that study results are biased.

We will request for waiver of consent as part of the project to obtain the necessary contact information (e.g., telephone number) of candidates for recruitment prior to them signing a consent. We believe that this research could not practicably be carried out without the waiver or alteration. This is because we will need to obtain the contact information (e.g., telephone number) of candidates for recruitment prior to them signing a consent. This is essential to discuss details about the study (e.g., eligibility determination) and/or to verify interest.

We will request alterations to the informed consent process to include incorporating specific elements of concealment as part of this research. We will withhold information regarding the type of treatment (Burst-SCS, KHFSCS, Sham SCS, 50 Hz SCS) and the order of treatment that the subjects will receive during the study (concealment). To reliably compare the effects of active vs. sham SCS in subjects receiving SCS therapy as part of their standard of care, it is essential that we withhold information regarding the type of treatment and the order of treatment the subjects receive during the study. This blinding could potentially avoid altering subject behavior during the blinded phase of the study thereby justifying its use in achieving the goals of this research.

We do not believe that the waiver or alteration would cause harm, insults, injury to relationships, loss of job or insurance, injury to their health or well-being, etc. Potential risks might be related to loss of patient confidentiality. However, we will minimize this risk through several procedures. For example, we will make sure that the patient-subject information (e.g., contact information) obtained from appointment logs or medical records is stored only on secure (UM) computers, and that this information is maintained in a password-protected computer program at all times. Furthermore, we will make sure that only study team members listed on the IRB application will have access to this information. Therefore, this criterion affirms the request for a waiver or alteration of the informed consent.

Screening

Potential subjects who are interested in participating in the study will be contacted by a member of the study team responsible for enrollment. Interested candidates will have the study and the eligibility criteria explained to them. If, at this point, they wish to continue with enrollment the candidate will be invited to participate in a study screening visit.

The screening visit begins with the informed consent interview. Once the subject has formally consented to participate (by either signing the consent electronically or in person) they will undergo a screening examination by a member of the study team. This includes:

- Completing demographic, sociodemographic, and medical history questionnaires
- Collecting and reviewing patient's pain rating and self-reported questionnaires and surveys
- Assessing fibromyalgia status by completing Fibromyalgia Symptom Questionnaire (FSQ)
- Conducting a physical assessment (height and weight) and collecting vital signs
- Completing and reviewing Psychological Screening questionnaires (HADS)
- Administering a urine pregnancy test to women of childbearing potential
- Documenting and reviewing current concomitant medications

Completion of these screening procedures will allow the study personnel to verify that the subject meets the full inclusion/exclusion criteria. For this study utilizing a single consent form, randomization should occur within two months of completing the screening procedures.

